9.6 Removal of Subjects

Subjects may withdraw from the study at any time at their own request. Subjects may be withdrawn from study drug treatment at any time at the discretion of the investigator or Vertex for safety, behavior, noncompliance with study procedures, or administrative reasons. If a subject has been withdrawn from study drug treatment, the subject should continue to be followed, provided the subject has not withdrawn consent.

Subjects who discontinue study treatment early should return for the Early Treatment Termination Visit and the Safety Follow-up Visit, as noted in Section 8.1.1.3.

If a subject does not return for a scheduled visit, reasonable effort will be made to contact the subject. In any circumstance, reasonable effort will be made to document subject outcome. The investigator will inquire about the reason for withdrawal, request that the subject return all unused investigational product(s), request that the subject return for the Early Treatment Termination Visit, if applicable, and Safety Follow-up Visit, if applicable (see Section 8.1.1.3), and follow up with the subject regarding any unresolved AEs.

If the subject withdraws consent, no further evaluations will be performed and no additional data will be collected. Vertex may retain and continue to use any data collected before such withdrawal of consent.

9.7 Replacement of Subjects

Subjects who withdraw or are withdrawn during the study drug treatment period(s) will not be replaced.

10 STUDY DRUG ADMINISTRATION AND MANAGEMENT

10.1 Preparation and Dispensing

Study drug may be dispensed only under the supervision of the investigator or an authorized designee to the subject's legally appointed and authorized representative (e.g., parent or legal guardian) for administration to the study subject.

10.2 Administration

Study drug tablets will be administered orally as shown in [Table 10-1](#). Subjects in the Observational Cohort will not receive study drug.

Table 10-1 Study Drug Administration

Treatment Cohort ^a	Time	LUM/IVA	LUM/IVA
		(100/125 mg per tablet)	(200/125 mg per tablet)
LUM/IVA (LUM 200 mg q12h/IVA 250 mg q12h) for subjects aged 6 through 11 years	AM	2 tablets	none
	PM	2 tablets	none
LUM/IVA (LUM 400 mg q12h/IVA 250 mg q12h) for subjects aged 12 years and older	AM	none	2 tablets
	PM	none	2 tablets

IVA: ivacaftor; LUM: lumacaftor; q12h: every 12 hours.

^a Subjects who turn 12 years of age in the previous study or Day 1 of this rollover study will begin receiving LUM 400 mg q12h/IVA 250 mg q12h on Day 1. Subjects who turn 12 years of age after the Day 1 Visit of the rollover study will begin receiving LUM 400 mg q12h/IVA 250 mg q12h at their next scheduled visit.

Study drug should be administered within 30 minutes of consuming fat-containing food such as a standard CF high-fat, high-calorie meal or snack according to the following guidelines:

- All doses of study drug (morning and evening, as applicable) should be administered at approximately every 12 hours (± 2 hour) on each dosing occasion (e.g., if the morning doses of study drug are administered at 08:00 hours on Day 1, all subsequent morning doses should be administered between 06:00 hours and 10:00 hours).
- For subjects at active sites who receive their last Study 109 dose at the Week 24 Visit, the Study 110 dose should be at least 6 hours after the Week 24 dose in Study 109; if the first Study 110 dose is not administered at the Study 109 Week 24/Study 110 Day 1 Visit, the first Study 110 dose will be the morning of the next calendar day.
- All subjects will be observed for 4 hours after the first dose of the study drug.
- On days of scheduled visits, with the exception of afternoon visits addressed below, the morning dose of study drug will be administered at the site after predose assessments have been completed. The meal or snack will be provided by the site for the morning dose of study drug.
- If a subject's scheduled visit is to occur in the afternoon, the following guidelines must be used for administering either the morning or evening dose:
 - If the dose in the clinic will be within 6 hours of the subject's scheduled morning dose, the subject should withhold their morning dose of study drug and the morning dose will be administered in the clinic.
 - If the dose in the clinic will be more than 6 hours after the subject's scheduled morning dose, the subject should take the morning dose at home and the evening dose will be administered in the clinic. In this event, all assessments will be collected relative to the evening dose.
- For visits after the Day 1 Visit, subjects will be instructed to bring all used and unused study drug to the site; study drug will be dispensed at each visit, as appropriate.
- At the Week 96 Visit, the last dose of study drug will be administered.

10.3 Method of Assigning Subjects to Treatment Groups

This is an open-label study. Randomization is not required because all subjects will be treated identically in the Treatment Cohort.

Subjects in the Observational Cohort will not receive study drug.

10.4 Study Drug Interruption

If study drug dosing must be interrupted for more than 72 hours, the medical monitor must be notified. In these instances, study drug dosing may only resume after approval by the medical monitor. Specific instructions for interruption for elevated LFT levels and elevated QTc levels are provided in Section 11.7.3 and Section 11.7.5.

10.5 Dose Modification for Toxicity

Modifications of the study drug dose are prohibited. If any unacceptable toxicity arises, study drug dosing will be discontinued for the individual subject (Section 8.1.1.3).

10.6 Packaging and Labeling

Vertex will supply the LUM 100-mg/IVA 125-mg tablets and LUM 200-mg/IVA 125-mg tablets in child-resistant weekly blister cards. Study drug labeling will be in compliance with applicable local and national regulations. Additional details regarding packaging, labeling, and dispensing for lumacaftor and ivacaftor will be included in the Pharmacy Manual.

10.7 Study Drug Supply, Storage, and Handling

Table 10-2 provides the study drug information. The investigator, or an authorized designee (e.g., a licensed pharmacist), will ensure that all investigational product is stored in a secured area, under recommended storage conditions, and in accordance with applicable regulatory requirements. To ensure adequate records, all study drugs will be accounted for as detailed in Section 10.8. Detailed instructions regarding the storage, handling, and dispensation of the study drug will be provided in the Pharmacy Manual.

Table 10-2 Study Drug

Drug Name	Formulation/ Route	Packaging (Formulation Strength)	Storage Condition
Lumacaftor/ivacaftor (fixed-dose)	Fixed-dose tablet/ Oral	Supplied as 100-mg lumacaftor/125-mg ivacaftor tablets	Store at $\leq 25^{\circ}\text{C}$ (77°F) with excursions to 30°C (86°F)
Lumacaftor/ivacaftor (fixed-dose)	Fixed-dose tablet/ Oral	Supplied as 200-mg lumacaftor/125-mg ivacaftor tablets	Store at $\leq 30^{\circ}\text{C}$ (86°F)

10.8 Drug Accountability

The pharmacist or designated study site staff will maintain information regarding the dates and amounts of (1) study drug received, (2) study drug dispensed to the subjects, and (3) study drug returned by the subjects. Subjects will be instructed to return all used and unused materials associated with the study drug to the site. These materials will be retained at

the site according to instructions provided by Vertex or its designee until inventoried by the study monitor. The study monitor will review study drug records and inventory throughout the study.

10.9 Disposal, Return, or Retention of Unused Drug

The study site staff or pharmacy personnel will retain all materials returned by the subjects until the study monitor has performed drug accountability. The site monitor will instruct the site when it is appropriate to return or destroy study drug. If the site monitor authorizes destruction at the study site, the investigator, or designee, will ensure that the materials are destroyed in compliance with applicable environmental regulations, institutional policy, and any special instructions provided by Vertex. Destruction will be adequately documented. Procedures for destruction or return of the study drug will be detailed in the Pharmacy Manual.

10.10 Compliance

To ensure treatment compliance, the investigator or designee will supervise all study drug dosing that occurs at the site. At each visit, site personnel will review that the subject is compliant with study drug dosing and remind the subject of study drug dosing requirements. Compliance will also be assessed by ongoing study drug count.

If a subject demonstrates continued noncompliance of study drug dosing despite educational efforts, the investigator should contact the medical monitor to discuss discontinuation of the subject from the study treatment. Subjects who prematurely discontinue study drug treatment during the Treatment Period in Study 110 will be asked to complete the Early Treatment Termination Visit and the Safety Follow-up Visit (Section 8.1.1.3).

10.11 Blinding and Unblinding

This will be an open-label study; however, subjects and their parent/caregiver should not be informed of their study-related LCI, spirometry, sweat chloride, [REDACTED] results during the study regardless if the subject has prematurely discontinued treatment or not.

11 ASSESSMENTS

11.1 Timing of Assessments

The timing of assessments is shown in [Table 3-1](#).

The following assessments must be performed in the order specified below when more than 1 assessment is required at a particular time point:

1. All questionnaires should be completed before the start of any other assessments scheduled at that visit. The CFQ-R should be completed first, followed by the TSQM.
2. Predose ECGs will be performed before any other procedures that may affect heart rate (e.g., blood draws).

3. The LCI assessment (performed for subjects from Study 109 and the Study 011B LCI Substudy only) should be performed before spirometry.

Additional timing notes

- The liver function testing at Weeks 12, 20, 60, and 84 may be completed pre- or postdose.
- The urine pregnancy tests at Weeks 12 and 20 may be completed pre- or postdose

11.2 Informed Consent/Assent

Subjects not of age of consent must assent, if applicable per local requirements, to participate in the study, and the subject's parent or legal guardian must sign and date a study-specific ICF before any study-specific procedures can be performed. The consent forms will comply with all applicable regulations governing the protection of human subjects. An ICF (and assent form, if applicable), approved by Vertex and the site's IRB/IEC, must be used.

11.3 Subject and Disease Characteristics

Subject and disease characteristics include the following: demographics, medical history, height, and weight. Select demographic and baseline characteristic data and medical history will be derived from the previous study.

Age, sex, race, and ethnicity will be derived from the previous study because these data are required for the normalization of spirometry values using the Wang method (Section 11.6.3).

11.4 Pharmacokinetics

Not applicable

11.6 Efficacy

11.6.1 Lung Clearance Index

The LCI assessment will be conducted for subjects from Study 109 and the Study 011B LCI Substudy only.

The LCI assessments, derived from N₂-multiple-breath washout (MBW) testing, will be conducted at visits specified in [Table 3-1](#) to evaluate the effect of lumacaftor in combination with ivacaftor on LCI and for evaluation of correlations between LCI and sweat chloride, and correlations between LCI and spirometry parameters. LCI_{2.5} represents the number of lung turnovers required to reduce the end tidal inert gas concentration to 1/40th of its starting value whereas LCI_{5.0} represents the number of lung turnovers required to reduce the end tidal inert gas concentration to 1/20th of its starting value.⁶¹

Each MBW will be performed in triplicate for each visit and the final LCI value will be calculated from the technically acceptable washout replicates by a central reader. The final LCI value at each visit will be the value provided by the LCI vendor based on the triplicates. The time for performing this test (in triplicate) during the study is approximately 1 hour at each study visit.

Pre-bronchodilator MBW testing is defined as MBW testing performed for subjects who have

- withheld their short-acting bronchodilator (e.g., albuterol) or anticholinergic (e.g., Atrovent) for more than 4 hours before the MBW testing;
- withheld their long-acting bronchodilator (e.g., salmeterol) more than 12 hours before the MBW testing; and
- withheld their once-daily, long-acting bronchodilator (e.g., tiotropium bromide [Spiriva[®]]) for more than 24 hours before the MBW testing.

All MBW testing should be performed “pre-bronchodilator.” During the Treatment Period, MBW testing must be performed before dosing, unless noted otherwise. In the event that a subject forgets to withhold bronchodilator(s), MBW testing should be performed according to the following:

- If a subject's Day 1 MBW testing is pre-bronchodilator, but on a subsequent visit, the subject forgets to withhold bronchodilator use, post-bronchodilator MBW testing will be obtained for that visit only, and the visit will not be rescheduled.
- If on Day 1, the subject forgets to withhold his/her dose of bronchodilator, MBW testing should be performed post-bronchodilator and all subsequent MBW testing (according to the Schedule of Assessments detailed for LCI in [Table 3-1](#)) should be performed post-bronchodilator.
- Each MBW test will be recorded in the source documents as pre-bronchodilator or post-bronchodilator.

The MBW testing should be performed before the spirometry assessment (Section [11.6.3](#)). Subjects and parents/caregivers should not be informed of study-related LCI results.

Detailed LCI procedures will be supplied in the Study Reference Manual.

Subjects and their parent/caregiver should not be informed of their study-related LCI results during the study regardless if the subject has prematurely discontinued treatment or not.

11.6.2 Sweat Chloride

The sweat chloride test is a standard diagnostic tool for CF, serving as a biomarker of CFTR activity. Collection of sweat samples will be performed at visits specified in [Table 3-1](#) using an approved collection device. Sweat samples will be sent to a central laboratory for testing and interpretation of results. Individual sweat chloride test results will not be disclosed to the study sites. Specific instructions for collection, handling, processing, and shipping of sweat chloride samples to the central laboratory will be provided separately. The sweat chloride test must be conducted predose relative to the morning dose of study drug during the Treatment Period. At each time point, 2 samples will be collected, 1 sample from each arm (left and right).

Subjects and their parent/caregiver should not be informed of their study-related sweat chloride results during the study regardless if the subject permanently discontinues treatment or not.

11.6.3 Spirometry

Spirometry will be performed according to the American Thoracic Society Guidelines⁶² at the time points noted in [Table 3-1](#) according to the additional guidelines that follow.

Pre-bronchodilator spirometry is defined as spirometry testing performed for subjects who have

- withheld their short-acting bronchodilator (e.g., albuterol) or anticholinergic (e.g., Atrovent) for more than 4 hours before the spirometry assessment;

- withheld their long-acting bronchodilator (e.g., salmeterol) more than 12 hours before the spirometry assessment; and
- withheld their once-daily, long-acting bronchodilator (e.g., tiotropium bromide [Spiriva[®]]) for more than 24 hours before the spirometry assessment.

All spirometry assessments should be performed “pre-bronchodilator.” During the Treatment Period, spirometry assessments must be performed before dosing, unless noted otherwise. In the event that a subject forgets to withhold bronchodilator(s), spirometry should be performed according to the following:

- If a subject's Day 1 spirometry from Study 109 or Study 011B is pre-bronchodilator, but on a subsequent visit, the subject forgets to withhold bronchodilator use, a post-bronchodilator spirometry will be obtained for that visit only, and the visit will not be rescheduled.
- If, on Day 1 of Study 109 or Study 011B, the subject forgets to withhold his/her dose of bronchodilator, spirometry should be performed post-bronchodilator and all subsequent spirometric measurements in Study 110 (according to the schedule of assessments detailed in [Table 3-1](#)) should be performed post-bronchodilator.
- Each spirometry assessment will be recorded in the source documents as pre-bronchodilator or post-bronchodilator.

The parameters listed below will be normalized using the standards of Wang et al.⁶³

- FEV₁ (L)
- Forced vital capacity (FVC) (L)
- FEV₁/FVC (ratio)
- Forced expiratory flow (FEF_{25%-75%}) (L/s)

All sites will be provided with spirometers and associated materials to be used for all study assessment by the central spirometry service. Spirometry data will be transmitted to a centralized spirometry service for quality review.

Subjects and their parent/caregiver should not be informed of their study-related spirometry results during the study regardless if the subject permanently discontinues treatment or not.

11.6.4 Weight, Height, and BMI

Weight and height will be assessed and BMI will be derived. Weight and height will be measured with shoes off at time points noted in [Table 3-1](#). Weight and height will be measured before the dose of the study drug during the Treatment Period.

11.6.5 Cystic Fibrosis Questionnaire-Revised

The questionnaires provide information about demographics; general quality of life, school, work, or daily activities; and symptom difficulties (pertaining to CF). Copies of the CFQ-R used in this study will be provided in the Study Reference Manual. Validated translations^{42,43} of the CFQ-R, if available, will be provided for participating centers in non-English-speaking

countries (if applicable). The CFQ-R should be completed before the start of any assessments scheduled at that visit.

Subjects will be asked to complete the CFQ-R in their native language, if validated translations are available.^{36,38} The CFQ-R will be completed before dosing at visits noted in [Table 3-1](#). At the Day 1 Visit of Study 110, subjects will complete the same version of the CFQ-R that was completed in the previous study (Study 109 or Study 011B). Subjects who are ≥ 12 years of age after the Day 1 Visit will complete the CFQ-R Child Version themselves, and their parents/caregivers will complete the CFQ-R Parent Version, on all visits, regardless of whether the subject subsequently turns 14 years of age during the study.

11.6.6 Treatment Satisfaction Questionnaire for Medication

Subjects will complete the TSQM before dosing at visits noted in [Table 3-1](#). The TSQM is a widely used generic measure of satisfaction with medication. The domains of the TSQM measure effectiveness, side effects, convenience, and global satisfaction. Because treatment satisfaction is not measured with the other health-related quality-of-life measures in this study, the TSQM will be included as a study assessment for this purpose. Translations of the TSQM will be provided for participating centers in non-English-speaking countries (if applicable). The TSQM must be completed after the CFQ-R and before the start of any other assessments scheduled at that visit.

Subjects should be instructed to complete the TSQM questionnaire on Day 1 based on their experience of their current medication regimen over the prior 2 to 3 weeks. For all subsequent visits, subjects should be instructed to complete the TSQM based on their experience of the study drug over the prior 2 to 3 weeks. Subjects who discontinue study drug permanently, or who have interrupted study drug, will still complete the TSQM based on their experience of the study drug if taken during the prior 2 to 3 weeks. If study drug was not taken during this period, the responses should be based on their experience of their current medication regimen.

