6.3 Other Secondary Endpoints

Treatment Cohort Period 1

The following efficacy endpoints are defined using baseline values in the previous study (i.e., Study 109 or Study 011B):

- Absolute change from baseline in LCI_{5.0} (subjects from Study 109 and Study 011B LCI Substudy only)
- Absolute change from baseline in ppFEV₁
- Relative change from baseline in ppFEV₁
- Absolute change from baseline in BMI-for-age z-score
- Absolute change from baseline in weight
- Absolute change from baseline in weight-for-age z-score
- Absolute change from baseline in height
- Absolute change from baseline in height-for-age z-score
- Absolute change from baseline in Treatment Satisfaction Questionnaire for Medication (TSQM) domains

The following efficacy endpoints are defined using baseline values in the current study (i.e., Study 110):

- Absolute change from baseline in LCI_{5.0} (subjects from Study 109 and Study 011B LCI Substudy only)
- Absolute change from baseline in ppFEV₁
- Relative change from baseline in ppFEV₁
- Absolute change from baseline in BMI-for-age z-score
- Absolute change from baseline in weight
- Absolute change from baseline in weight-for-age z-score
- Absolute change from baseline in height
- Absolute change from baseline in height-for-age z-score
- Absolute change from baseline in TSQM domains

The following pulmonary exacerbation-related endpoints are defined for subjects from Study 109 only:

- Time-to-first pulmonary exacerbation, including pulmonary exacerbations in the previous study and the current study
- Event of having at least 1 pulmonary exacerbation, including pulmonary exacerbations in the previous study and the current study
- Number of pulmonary exacerbations, including pulmonary exacerbations in the previous study and the current study

The following efficacy endpoints are also defined:

- Rate of change in LCI_{2.5} (subjects from Study 109 and the Study 011B LCI Substudy only)
- Rate of change in LCI_{5.0} (subjects from Study 109 and the Study 011B LCI Substudy only)
- Rate of change in ppFEV₁

Treatment Cohort Period 2 and Observational Cohort

Not applicable

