10.3.2.2 Analysis of Secondary Endpoints

10.3.2.2.1 Analysis of Secondary Endpoints

The analysis of secondary efficacy endpoints will be conducted for the Treatment Cohort Period 1 only.

Absolute change from baseline in LCI_{2.5}

The analysis for efficacy endpoints will be focused on within-group comparison and summaries. No between-groups comparisons will be performed.

For Treatment Cohort Period 1, the mixed model repeated measures (MMRM) analysis will be used for the Cumulative Study Period based on the FAS. It will include two treatment groups (L200/I-L/I and P-L/I) using baseline of the Previous Study Period.

The absolute change from previous study baseline (including all measurements at each visit, both on-treatment measurements and measurements after treatment discontinuation), will be included as the dependent variable; treatment group, visit, and treatment-by-visit interaction, as fixed effects; and subject as a random effect with adjustment for previous studies (Study 109 versus Study 011B), weight (<25 kg versus \geq 25 kg), and ppFEV₁ severity (<90 versus \geq 90), both as determined at screening in the previous studies, and previous study baseline LCI_{2.5} as a continuous variable.

In the model, visit will be treated as a class variable, and an unstructured covariance matrix will be assumed to model the within-subject variability. This model imposes no assumptions on the correlational structure and is considered robust. If there is a convergence problem due to the unstructured covariance matrix, the unstructured covariance matrix will be replaced by compound symmetry in the primary analysis. Denominator degrees of freedom for the *F*-test for fixed effects will be estimated using the Kenward-Roger approximation.¹ With a mixed-effects model as the primary analysis model based on restricted maximum likelihood estimation and assuming that conditional on fixed and random effects data are missing at random, no imputation of missing data will be done.

The result obtained from the model will be the treatment effect at each post baseline visit. The estimated mean within-group treatment effect, i.e., Least Square (LS) Means, SE, 95% CI, and a 2-sided within treatment group *P* value, will be provided. The LS means of absolute change from previous study baseline with 95% CI at each visit during the Cumulative Study Period will be plotted by treatment groups (L200/I-L/I and P-L/I).

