The analysis of height and height-for-age Z-score will be similar to those specified for the MMRM analysis of LCI_{2.5}, with the absolute change from previous study baseline in height or height-for-age z-score, respectively, at each visit as the dependent variable; and replacing the baseline LCI_{2.5} with baseline height or height-for-age z-score of the previous studies, respectively, as a continuous covariate. Figure for height and height-for-age Z-score will be

plotted similar to absolute change in LCI_{2.5} above. Descriptive summary based on the current study baseline for P-L/I, similar to the summary of LCI_{2.5}, will be provided separately.

Absolute change from baseline in TSQM domains

For TSQM domains, the analysis will be similar to those specified for the MMRM analysis of LCI_{2.5}, with the absolute change from previous study baseline in each domain at each visit as the dependent variable; and replacing the baseline LCI_{2.5} with domain baseline of the previous studies as a continuous covariate. Descriptive summary based on the current study baseline for P-L/I, similar to the summary of LCI_{2.5}, will be provided separately.

Number of pulmonary exacerbations (109 Subjects Only)

The number of pulmonary exacerbations will be analyzed using negative binomial regression model (PROC GENMOD) with two treatment groups: L200/I-L/I based on 109 FAS including events in the Cumulative Study Period, and P-L/I based on 109 ROS including events in the Current Study Period. All pulmonary exacerbation events in each corresponding Study Period will be included.

The model will include treatment (L200/I-L/I and P-L/I), weight (<25 kg and ≥25 kg) and ppFEV₁ severity at screening of the previous study (<90 versus ≥90). The log of time spent for each Study Period (end date of the Study Period – first dose date of the corresponding Study Period +1) in patient-years will be treated as the offset in this model.

The data during the placebo-controlled period for subjects randomized to the placebo group in Study 109 will be analyzed using a similar negative binomial regression model without the treatment in the model. Note the placebo rate might be slightly different from that estimated in Study 109 final CSR analyses, which included two arms (placebo and active) instead of the placebo arm only in this model.

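### The TSQM model keeps off-drug ratings of a different regimen and reports them as the treatment effect, chiefly at the Safety Follow-up Visit

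*Protocol*

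**What the plan says.** Protocol 11.6.6 gives the TSQM three possible objects of rating.

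- On Study 110 Day 1, with a recall of two to three weeks: "Subjects should be instructed to complete the TSQM questionnaire on Day 1 based on their experience of their current medication regimen over the prior 2".
- After that, with the same recall: "For all subsequent visits, subjects should be instructed to complete the TSQM based on their experience of the study drug over the prior 2 to".
- When off drug: "If study drug was not taken during this period, the responses should be based on their experience of their current medication regimen".

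SAP 6.3 lists "Absolute change from baseline in TSQM domains" among the other secondary endpoints, once against the previous-study baseline and once against the Study 110 baseline. SAP 10.3.2.2.2 models TSQM on the LCI2.5 pattern, "with the absolute change from previous study baseline in each domain at each visit as the dependent variable". For the covariate it specifies "replacing the baseline LCI_{2.5} with domain baseline of the previous studies as a continuous covariate". The LCI2.5 model in SAP 10.3.2.2.1 takes in "both on-treatment measurements and measurements after treatment discontinuation". It presents each post-baseline visit's within-group LS mean, with 95% CI and two-sided P value, as the treatment effect. The Study 110 baseline is used for TSQM only descriptively, and only in P-L/I.

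The schedule in SAP Appendix A (Table 13-1) includes TSQM at the Safety Follow-up Visit, 4 weeks (± 7 days) after the last dose. SAP Appendix D (Table 13-5) maps a Follow-up nominal visit for TSQM. The SAP has no rule that flags, excludes or separates TSQM records that do not rate study drug.

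**The concern.** Keeping measurements after discontinuation is sensible for LCI or weight, because the quantity means the same thing on or off drug. It does not carry over to a questionnaire whose subject changes when the drug stops. An off-drug TSQM score is, by the protocol's own instruction, a rating of some other regimen. Averaging it with ratings of study drug, or testing it alone at a follow-up visit, gives an LS mean and P value headed as a treatment effect that partly or wholly describe a different medicine.

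The baseline needs a related label. The previous-study baseline comes before any LUM/IVA, so even a clean on-drug change compares study drug with whatever preceded it. At stake is the reading of all four TSQM domains under the long-term efficacy and durability objective.

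**Working it through.** The documents give no sample size, effect size, SD or dropout figure for TSQM, so there is no planned figure to reproduce. The check traces which records enter the model and what each one rates.

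1. **Baseline.** SAP 10.1 defines baseline as the latest measurement before the first dose of the Study Period. The previous-study baseline therefore cannot rate LUM/IVA for anyone. This follows from timing alone, because the Study 109 and 011B Day 1 instructions are not in these documents.

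2. **Safety Follow-up.** Days off drug: 28 ± 7 = 21 to 35. Recall: 14 to 21 days. Study-drug days in the recall window = max(0, recall − days off drug).
   - 21 days off: max(0, 14 − 21) = 0 and max(0, 21 − 21) = 0.
   - 28 and 35 days off: 0 for both recall lengths.

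   So the reversion rule applies at this visit even to subjects who completed treatment.

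3. **Study 011B washout (Week 24 to Week 26).** About 14 days off drug leaves max(0, 14 − 14) = 0 to max(0, 21 − 14) = 7 drug days in the window. If TSQM was taken at Week 26, it is a borderline record.

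4. **Other routes into the model.**
   - Subjects who stopped drug in a parent study but stayed to its final visit (Protocol 9.1, Observational Cohort) are in the FAS, which SAP 8.1 defines by dosing in the parent study.
   - Interruptions longer than the recall period also produce off-drug ratings.
   - An Early Treatment Termination Visit occurs less than 3 weeks after the last dose, since Safety Follow-up replaces it from 3 weeks on. One held 14 to 20 days after the last dose is off drug under a 2-week recall and on drug under a 3-week recall.

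5. **P-L/I in Study 109.** Study drug was placebo, so on-treatment ratings in that period concern placebo (assuming Study 109 gave the same later-visit instruction).

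6. **Size.** Let f be the share of a visit's records with no study drug in the recall window. For a simple visit mean,

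   mean change = (1 − f)(S_drug − S_base) + f(S_other − S_base).

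   The scores below are assumed, not taken from the documents: S_drug = 75, S_base = 55, S_other = S_base.

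   | f | Mean change |
   |---|---|
   | 0 | +20 |
   | 5% | +19 |
   | 10% | +18 |
   | 20% | +16 |
   | 100% | 0 |

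   The last row is the Safety Follow-up case. With f = 0 and S_drug held at 75, baseline-regimen scores of 55, 65, 75 and 85 give changes of +20, +10, 0 and −10. The sign depends on how the pre-treatment regimen was rated.

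**The case against.** The strongest reply is that the on-treatment results are largely sound, and most of that stands.

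- **Follow-up is a separate visit level.** Visit is a class variable with a treatment-by-visit interaction, so the Safety Follow-up estimate does not enter the Week 4 to Week 96 means.
- **Off-drug records elsewhere should be few.** In Study 110, subjects who stop treatment are scheduled only for the termination and follow-up visits.
- **Durability contrasts survive the baseline issue.** The model adjusts for baseline with no baseline-by-visit term. Modelling change or post-baseline score therefore gives the same differences between visits; only the baseline coefficient shifts by 1.
- **Raw scores are already planned** by visit (Protocol 12.4.3; SAP Table 10-2), although not limited to on-drug ratings.
- **Consequences are limited.** This is an other secondary endpoint in an open-label safety study, without between-group comparison and with nominal P values (SAP 10.3.2.3).
- **Follow-up is not universal.** It is waived for subjects who stop early and go straight to commercial LUM/IVA, and for those entering Treatment Cohort Period 2. A completer who moved to commercial supply could still have LUM/IVA in the current regimen.

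A reader might infer from the Day 1 instruction that the modelled baseline is a rating of other medicines. The documents do not support this. That sentence governs Study 110 Day 1, while the model uses the previous-study baseline. A former active-arm Study 109 subject who rolls over without interruption would normally have LUM/IVA in the Day 1 regimen. A reader might also infer that the change score says nothing about satisfaction with LUM/IVA, or that its P values must go. On-drug scores do rate study drug, and their change from baseline is a comparison with the pre-treatment regimen. Dropping the P values is a matter of preference.

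None of this answers the Safety Follow-up estimate, or the absence of any rule for off-drug ratings at other visits.

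**Conclusion.** The point holds in a limited form. At Safety Follow-up, the TSQM LS mean and P value normally describe a regimen other than study drug but would be reported as its effect. At other visits any off-drug records dilute the on-drug estimate by an amount the documents do not allow to be computed; it is probably small. On-drug change is satisfaction with study drug relative to the pre-treatment regimen, not a change in satisfaction with LUM/IVA, and the SAP does not say so.

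The conclusion assumes that subjects follow the Protocol 11.6.6 instruction, that including all measurements at each visit covers the mapped Follow-up visit, and, for parent-study discontinuers, that Studies 109 and 011B used the same reversion rule. Neither the safety conclusions nor the main secondary endpoints are affected. This is an inexpensive improvement.

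**What to change.** Amend the TSQM paragraph of SAP 10.3.2.2.2 as follows.

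1. Restrict the TSQM MMRM to post-baseline records with study drug taken within the protocol's recall window. State which end of the 2-to-3-week range defines it; 21 days with a 14-day sensitivity run would cover both. Derive the flag from dose and interruption dates, which SAP 10.2.4 and 10.2.5 already use.
2. Move Safety Follow-up and all other off-drug ratings, including any at Study 011B Week 26 that fail the rule, to a separate descriptive table labelled as ratings of the current medication regimen.
3. Label P-L/I ratings during Study 109 as ratings of placebo.
4. Keep change from baseline, described as relative to the pre-treatment regimen, and show the planned raw domain scores by visit beside it for the same on-drug records.

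The cost is SAP wording and one derived flag, with no new data. The Protocol 12.4.3 MMRM is specified only for LCI and ppFEV1, and similar analyses of other variables are optional there, so the restriction does not conflict with it. The downside is that a small number of off-drug records leave the model.
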